8.2. Primary objectives

The primary objectives of the Registry are to:

1. Monitor the pattern of use and record utilisation information:
 - the proportion of patients exposed to aprotinin in accordance with the authorized indication
2. Measure the incidence of the following adverse events:
 - death and the distribution of the primary cause of death
 - thromboembolic events; the total and individual incidence of myocardial infarction, stroke and other thromboembolic events recorded
 - incidence of renal dysfunction defined as a rise in creatinine from pre-operative to post-operative levels of > 0.5 mg/L, and the incidence of renal dialysis
 - the numbers having an anaphylactic response to aprotinin
3. Measure the effectiveness of risk minimisation measures as described in the RMP and close monitoring of adherence to the SmPC recommendations:
 - the proportion of patients receiving heparinisation monitoring as recommended in the SmPC
 - Proportion of patients with a minimal ACT-celite below 750 seconds
 - Proportion of patients with a minimal ACT-kaolin below 480 seconds
 - the proportion of patients with a post-operative renal dysfunction defined as a rise in creatinine from pre-operative to post-operative levels of > 0.5 mg/L or requiring dialysis known to have received aminoglycoside antibiotics
 - the proportion of patients exposed to aprotinin without the use of test dose (or antibody test)
 - the proportion of patients administered with the recommended posology
 - the proportion of patients administered with less than 2.5 million KIU
 - the proportion of patients administered with more than 7 million KIU

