9.3.4. Aprotinin use *

The reason for using aprotinin;
Prior exposure to aprotinin or to fibrin sealants (some contain aprotinin), if available;
Aprotinin IgG test and result if available;
Administration of the test dose to aprotinin and the reaction to the test dose (including anaphylactic reaction);
The loading dose of aprotinin, the pump priming dose and the continuous infusion dose;

The use of another haemostatic.

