9.3.5. Intra-operative coagulation and blood loss monitoring in the operating room*

Coagulation prevention details, dose of heparin, either fixed or by titration, before and during surgery;

Monitoring of anti-coagulation, ACT, kaolin or celite;

The minimum operative ACT when available;

The estimated intra-operative blood loss, if available;

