As a matter of fact imputation of data is more or less invention of data that can strongly bias results in an observational study. The less speculative approach is therefore to remove from the data patients without the needed information from the analysis.

In data modelling or if a breakdown of the sample is done according a given variable, a missing data in any qualitative covariate (or factor of segmentation of the sample) can have a category called "unknown". A first model will fitted with such a categorization and a second one will be fitted after removing all patients with missing data on the covariate. If it concerns a breakdown of the sample then descriptive statistics along with 95% confidence interval will be provided for all categories including the unknown class. Regarding quantitative covariate, categorization of the covariate may be done and a first model will be fitted with only categorical variables including the "unknown" category and a

second model is fitted with quantitative covariate (patients with a missing data are excluded). Concerning the breakdown the same categorization approach will be applied and estimation will be provided for each category. If a breakdown of the sample is applied the estimation for the "unknown" category will be compared to all the other categories combined to assess whether missing data represent approximately the average of the collected data.

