Annex 1. DHPC

15 September 2015

New indication and safety information for aprotinin (Trasylol®), following its re-introduction to the market

Dear Health Care Professional,

Summary

Aprotinin (Trasylol®) will be re-introduced in your country from [date to be confirmed] with a restricted indication and new safety information as follows:

New restricted indication for aprotinin (Trasylol®):

Aprotinin is indicated for prophylactic use to reduce blood loss and blood transfusion in adult patients who are at high risk of major blood loss undergoing isolated cardiopulmonary bypass graft surgery (i.e. coronary artery bypass graft surgery that is not combined with other cardiovascular surgery).

Aprotinin should only be used after careful consideration of the benefits and risks, and the consideration that alternative treatments are available.

New safety information:

The reduced level of heparinisation in the patients treated with aprotinin increases the risk of thrombotic events in this population. The level of heparinisation of patients is incorrectly interpreted with the use of non-appropriate activated clotting tests.

The data illustrates the risks associated with inadequate monitoring of the anticoagulative effect of heparin administered in the CABG procedure.

Aprotinin is not a heparin-sparing agent and it is important that adequate anticoagulation with heparin be maintained during aprotinin-therapy. Elevations in the partial thromboplastin time (PTT) and celite Activated Clotting Time (Celite ACT) are expected in aprotinin-treated patients during surgery, and in the hours after surgery. It is important that adequate anticoagulation with heparin be maintained and monitored during aprotinin treatment. In patients undergoing cardiopulmonary bypass who are being treated with aprotinin, one of the following three methods is recommended to maintain adequate anticoagulation:

- Activated Clotting Time (ACT)
- Fixed Heparin Dose
- Heparin Titration

Partial Thromboplastin Time (PTT) should not be used to maintain adequate anticoagulation with heparin.

An ACT is not a standardized coagulation test, and different formulations of the assay are affected differently by the presence of aprotinin. The test is further influenced by variable dilution effects and the temperature experienced during cardiopulmonary bypass. It has been observed that kaolin-based ACTs are not increased to the same degree by aprotinin as are diatomaceous earth-based (celite) ACTs.

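### Deleting patients with missing information (section 9.7) can overstate SmPC adherence under primary objective 3 where a check that was not recorded was not done

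*Protocol*

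**What the plan says.** Protocol section 8.2 makes adherence to the SmPC part of the primary objectives (objective 3). Three measures matter here. One is "the proportion of patients exposed to aprotinin without the use of test dose (or antibody test"). Another is "the proportion of patients receiving heparinisation monitoring as recommended in the SmPC". Under the latter stand two ACT thresholds, one per assay, the first being "Proportion of patients with a minimal ACT-celite below 750 seconds".

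The source fields are in 9.3.4 and 9.3.5, both key pages. Whether the test dose was given is listed without qualification. The antibody test is qualified: "Aprotinin IgG test and result if available". So is the lowest ACT value: "The minimum operative ACT when available". The heparin dosing method and the type of ACT monitoring are separate items without that qualifier.

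Under *Missing data*, 9.7 rejects imputation and sets a general rule: "The less speculative approach is therefore to remove from the data patients without the needed information from the analysis". It allows an unknown category, but for covariates and for the factors used to split the sample, not for the measure being estimated. The protocol does not give the denominators of the adherence proportions, and does not say whether a blank in these fields counts as not done or as missing.

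**The concern.** For most outcomes a blank is simply an unknown value. For an adherence measure the blank may itself be the failure: the test was not done, or the ACT was not checked. Deletion then takes likely failures out of both numerator and denominator. Section 9.7 presents deletion as the less speculative choice, but for a proportion it assumes that unrecorded patients behave like recorded ones. The protocol gives reason to doubt this: 9.3 expects incomplete entry even on key pages, and 9.9 accepts a risk of social desirability bias where the treating person enters the data.

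At stake is a primary objective that asks whether the risk minimisation measures are being followed. The exact 95% confidence intervals planned in 9.7 reflect sampling error only, so a shifted figure could be reported with a narrow interval.

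**Working it through.** **The plan's own precision.** Section 9.5 gives 3,951 analysable patients for a 1.56% margin at a proportion of 50%. Check: 1.96² × 0.25 / 0.0156² = 3,946.3, so 3,947 patients; at 3,951 the margin is 1.559%. Allowing for 25% exclusions, 3,951 / 0.75 = 5,268. Both figures reproduce. The protocol gives no figure for adherence or for missing ACT or IgG values, so the shares below are assumptions.

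**Test dose or antibody test.** A recorded test dose settles a patient's status whatever the IgG field says. A recorded *no test dose* does not: the IgG field is then needed. If a blank there is treated as missing, the patient is deleted. Let *t* be the share given a test dose, *a* the share antibody-tested among the rest, and *m* the share with a blank IgG field among the rest, with blanks unrelated to whether the test was done.

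- True share with neither test: (1 − t)(1 − a).
- Share reported after deletion: (1 − t)(1 − m)(1 − a) / [1 − (1 − t)m].

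With t = 0.80 and a = 0.05 the true share is 0.20 × 0.95 = 19.0%.

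| Blank IgG field (m) | Calculation | Reported |
|---|---|---|
| 20% | 0.152 / 0.96 | 15.8% |
| 50% | 0.095 / 0.90 | 10.6% |
| 90% | 0.019 / 0.82 | 2.3% |

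If blanks are not random, the direction reverses only when the untested share among deleted patients is below the reported figure. At these three reported figures, more than 84.2%, 89.4% or 97.7% of the deleted patients (100% minus each) would have to have been antibody-tested.

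**ACT thresholds.** Let *m* now be the share of ACT-managed patients with no recorded minimum, A_obs the share at or above threshold among recorded patients, and A_mis the same share among unrecorded patients.

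- Bias of the complete-case figure: m × (A_obs − A_mis).
- Bounds on the true figure: A_obs(1 − m) to A_obs(1 − m) + m.

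| A_obs | m | Lower bound | Upper bound |
|---|---|---|---|
| 90% | 5% | 85.5% | 90.5% |
| 90% | 10% | 81.0% | 91.0% |
| 90% | 20% | 72.0% | 92.0% |
| 70% | 20% | 56.0% | 76.0% |

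At A_obs = 90% and m = 20%, the complete-case figure is 18 points too high if A_mis = 0, 8 points too high if A_mis = 50%, right if A_mis = 90%, and 2 points too low if A_mis = 100%. For scale, the sampling margin at 90% with 0.8 × 3,951 = 3,161 patients is 1.96 × √(0.9 × 0.1 / 3,161) = 1.05 points. It would be wider within one assay.

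The 20% is only illustrative. The change table in section 5 speaks of a target above 80% for complete key data overall, which says nothing specific about ACT or IgG.

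**The case against.** A reader might infer that the rule works in one direction only and overstates adherence by construction. The documents do not support that, for four reasons.

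- The qualifier on the IgG field can be read as an instruction to enter a test if there was one. A blank then means no test, and a patient with no test dose and a blank IgG field stays in as untested.
- The test-dose field may itself be blank. A patient who had a test dose but has both fields blank is adherent, and is deleted too.
- Monitoring method is collected apart from the ACT value, so a patient recorded as unmonitored still lowers the heparinisation measure. Nor is a missing ACT non-adherence in itself: of ACT, fixed heparin dose and heparin titration, the letter to healthcare professionals in Annex 1 says that "one of the following three methods is recommended to maintain adequate anticoagulation".
- An unrecorded ACT could lie on either side of its threshold, so the 72% is a bound, not an estimate.

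All four stand, and they limit the claim to what can happen.

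It can also be said that the matter is already in hand. Section 9.9 will assess missing counts for key variables, 9.6 describes pop-ups and completeness flags, and the SAP (Annex 6, not shown) may define denominators and the coding of blanks. Counts show the gap but leave the estimate as it is, and the flags accept that incomplete records exist. What the SAP may settle is no finding here. The finding is the general rule that the protocol does state, which makes no exception for measures where a blank may be the failure.

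**Conclusion.** The point holds as a risk, not as a certainty. As worded, the 9.7 rule reaches primary adherence measures whose source fields are filled only when available, and it can overstate adherence where not recorded means not done.

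- **Test dose or antibody test.** If test-dose status is recorded and a blank IgG field is treated as missing, deletion falls only on patients without a test dose. Under the assumptions above, a true 19.0% with neither test would be reported as 15.8%, 10.6% or 2.3%. If blanks are read as no test, this error does not arise, but 9.7 does not say so.
- **ACT thresholds.** The sign depends on how unrecorded patients were managed, which the documents do not tell. At high observed adherence the upward error can be much the larger: with an assumed 20% missing and 90% observed, from +18 to −2 points. Even the 8 points that arise when half of the unrecorded patients were adequate exceed the 1.56-point margin in 9.5.

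**What to change.** In 9.7, exempt the objective 3 adherence measures from plain deletion and state how they are counted:

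- Use all exposed patients as the denominator; for the ACT thresholds, use ACT-managed patients on bypass, by assay.
- Count patients with neither a test dose nor an antibody test recorded as *no test documented*, rather than deleting them.
- Report three classes: documented adherent, documented non-adherent, not documented.
- Beside the complete-case proportion, show the two bounds, with all undocumented patients counted as adherent and then as non-adherent.

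Which of these figures leads the table is a matter of preference. Making documented adherence over all patients the headline would treat every blank as a failure and could err the other way. What matters is that the bounds stand next to the complete-case figure.

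The cost is a change of wording in 9.7, matching text in the SAP if it is not already there, and one extra column per adherence table. No new data are needed. The downside is a wider and less favourable range.

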9.5. Study size

All patients exposed to Nordic Aprotinin, at all participating cardiac surgical centres in European countries with marketing authorisation, are intended to be included during the study.

The study is designed primarily to monitor the pattern of use and record utilisation information such as the proportion of patients exposed to aprotinin in accordance with the authorized indication.

Considering that the registry of Great Britain & Ireland recorded just over 400,000 operations in 5 years and that the US one collected around 280,000 operations/year^{15,16}, we could postulate that, across Europe, at least 300,000 patients are undergoing cardiac surgery.

Thus, we estimate the sample size based on the occurrence of events of specific interest (such as type of procedure, death, thromboembolic, stroke ...) with a reasonable precision.

To obtain 95% confidence interval with a maximum margin error of 1.56%, 3,951 patients should be included. This margin error is the maximum one that can be obtained: it is the one based on the assumption that an event of interest is observed in 50% of patients (meaning a 95% CI of [48.44% ; 51.56%]). In all other cases (i.e. event of interest observed in less or more than 50%), precision will only be better (less than 1.56%).

There is no a priori calculation of power for this study because the main primary objective is descriptive rather than inferential and because the adverse event included in the other primary objectives such as in-hospital mortality, thromboembolic events or renal dysfunction are dependant of aprotinin's pattern of use.

Taking into account an exclusion rate of 25% (patient refusing data collection, un-exposed to aprotinin in the course of cardiac surgery with CPB, or undergoing off pump surgery), the number of patients to include is 5,268.

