9.7. Data analysis

All data analyses will be performed by Dendrite Clinical Systems together with Nordic after the Key Data are completed. Statistical programming and analyses will be performed using SAS and/or other statistical software as required.

Analysed data will be reviewed by an Independent Data Safety Monitoring Committee, involving at least four (4) national coordinating investigators.

The Registry will collect information for all patients who receive Nordic Aprotinin for any purpose in participating countries in Europe. The Registry will not allow a direct comparison of mortality and morbidity among patients treated with aprotinin to patients not with aprotinin. Mortality and morbidity outcomes vary according to patient selection criteria by centre and by country of treatment. Historical controls are not wholly reliable as patient selection and operative techniques vary over time. It is proposed to examine external data bases for comparative purposes as these may be used as a yardstick to measure patient outcomes, e.g. reports from existing national or European cardiac surgical databases. These external data will be mentioned in the Statistical Analysis Plan (SAP) prior to the first analysis.

The analysis of data from the Registry will be descriptive, and all information will be reported in summary tables.

The intention is to focus on those variables most pertinent to assessing compliance with approved labelling, including compliance with the approved indication, and compliance with instructions for appropriate use, including use of heparin and monitoring of anticoagulation. Summary data will be provided for all variables collected and the data will be reported overall, by country, and if required by centre.

The first data analyses will be conducted six months after the completion of data entry of the first subject in the study depending on PSUR scheme and timelines and will be repeated six months later. Thereafter the analyses will be conducted annually until the close of the Registry (i.e. for at least three years). Overall reports will be synchronised between each country so that **the analyses are all conducted at the same time.**

Analysis will be made of the data for Nordic Aprotinin overall, by individual country and if required by individual site. The analysis will include the following key outcomes and variables will be presented:

The outcomes to be included in each report will include at least:

- Death

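### If modelling is done, the missing-covariate rule in section 9.7 uses an 'unknown' level that can leave confounding in, and for quantitative covariates it changes patients and coding together

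*Protocol*

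**What the plan says.** The missing-data paragraph of protocol section 9.7 starts from a complete-case rule and rejects imputation: "The less speculative approach is therefore to remove from the data patients without the needed information from the analysis". It then provides for models and breakdowns.

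- **Qualitative covariate.** Missing values can form a category of their own. "A first model will fitted with such a categorization and a second one will be fitted after removing all patients with missing data" on that covariate. The coding of the observed levels does not change between the two.
- **Quantitative covariate.** "categorization of the covariate may be done and a first model will be fitted with only categorical variables including the 'unknown' category"; the "second model is fitted with quantitative covariate (patients with a missing data are excluded". Both the patient set and the coding change.
- **Breakdowns.** The unknown class is set against all other classes combined "to assess whether missing data represent approximately the average of the collected data". This is the only comparison in the paragraph with a stated purpose. Nothing says how to read agreement or disagreement between the two models, or which one is the result.

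The same section limits the role of modelling: "The analysis of data from the Registry will be descriptive, and all information will be reported in summary tables".

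**The concern.** Fitting one model with all patients and one with complete cases looks like a way to see whether missing values matter. As written, the pair cannot show that cleanly, for two reasons.

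1. **'Unknown' as an adjustment level.** Within that level the covariate is not held constant, so those patients contribute an association unadjusted for it. The first model's estimate is roughly a mixture of an adjusted and an unadjusted one, even if values are lost purely by chance.
2. **Two changes at once (quantitative covariates only).** Moving from categories to the quantitative form changes how much confounding is removed, whoever is missing.

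The stake is any adjusted association reported under this rule, for example in the further analyses that section 9.7 allows on request. Since the section does not say which model prevails, the less well adjusted one could be reported as the result.

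**Working it through.** **The plan's own figures (section 9.5).** "To obtain 95% confidence interval with a maximum margin error of 1.56%, 3,951 patients should be included". Half-width at p = 0.5: 1.96 × √(0.25/3,951) = 1.559%. Solving for 1.56% gives 3,947, close to the stated number, and 3,951/0.75 = 5,268. Both figures reproduce, and neither enters the argument below except as a realistic sample size.

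**Inputs.** The two model forms come from section 9.7. The protocol does not give the strength of confounding, the share missing per covariate or the number of categories, so these are assumptions: log-OR per SD of the covariate on both factor and outcome of 0.8 or 0.4; 0% to 40% missing completely at random; a median split, quartiles, or three qualitative levels. As a loose anchor for the share missing, the change table in section 5 reports complete key data above 80%.

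**Method.** Logistic simulation with a true factor OR of 1, so any departure from 1 beyond noise is residual confounding. A bridging model that is not in the protocol (same categories, complete cases) separates the two changes.

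**Limiting values, n = 1,000,000, log-OR 0.8 (factor intercept −0.5, outcome intercept −2.2):**

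| Covariate | Missing | Model 1 | Bridging | Model 2 |
|---|---|---|---|---|
| Quantitative, quartiles | 0% | 1.095 | 1.095 | 1.002 |
| Quantitative, quartiles | 20% | 1.200 | 1.090 | 1.000 |
| Quantitative, median split | 0% | 1.237 | 1.237 | 0.998 |
| Quantitative, median split | 20% | 1.326 | 1.239 | 0.995 |
| Qualitative, 3 levels | 10% | 1.070 | 1.007 | 1.007 |
| Qualitative, 3 levels | 20% | 1.128 | 1.005 | 1.005 |
| Qualitative, 3 levels | 40% | 1.253 | 0.998 | 0.998 |

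The 0% rows show the coding effect alone. The qualitative rows show the 'unknown' effect alone. Other runs with quartiles at the same strength and share missing, including runs with a rarer factor and outcome (intercepts −1.4 and −3.2), gave 1.23 to 1.25 for model 1 against 0.99 to 1.00 for model 2.

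**Hand check of the mechanism.** In the rarer-outcome setting the crude OR is 1.75, and the complete-case categorical OR is 1.13 (four categories) or 1.30 (two). Weighting 80% adjusted and 20% crude on the log scale:

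- four categories: 0.8 × ln 1.13 + 0.2 × ln 1.75 = 0.098 + 0.112 = 0.210, OR 1.23 (simulated 1.23);
- two categories: 0.8 × ln 1.30 + 0.2 × ln 1.75 = 0.210 + 0.112 = 0.322, OR 1.38 (simulated 1.37).

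**At the registry's size, n = 3,951, 800 runs, quantitative covariate.** The gap is the log-OR of model 1 minus that of model 2; parts may not sum exactly because of rounding.

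| log-OR, coding, missing | Mean gap | From 'unknown' | From coding | SD of gap | Model 1 higher |
|---|---|---|---|---|---|
| 0.8, quartiles, 20% | 0.188 | 0.100 | 0.088 | 0.060 | 99.9% |
| 0.8, median split, 20% | 0.282 | 0.064 | 0.217 | 0.065 | 100% |
| 0.8, quartiles, 5% | 0.114 | 0.025 | 0.089 | 0.035 | 100% |
| 0.4, quartiles, 20% | 0.045 | 0.023 | 0.023 | 0.057 | 78% |
| Covariate unrelated to factor | −0.001 | −0.001 | 0.000 | 0.055 | 48% |

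At log-OR 0.4 the gap is a ratio of exp(0.045) = 1.05 and is smaller than its own sampling variation.

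**The case against.** The strongest reply is that little depends on this clause. Section 9.5 calls the main primary objective descriptive, section 9.7 plans summary tables with exact confidence intervals, and no adjusted model is named. The updated ENCePP checklist (Annex 3) answers No on measures of association (3.4) and N/A on control of confounding (10.5). The modelling text is conditional throughout. All of this stands and limits the weight of the point.

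The second model is also already a complete-case fit with the quantitative covariate, and it recovers the true value in the simulations. The sounder estimate would therefore appear beside the weaker one. That stands too, but the section does not say which is the main model.

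The larger gaps need strong confounding. If the 80% figure refers to records, any single key covariate is missing in fewer than 20% of patients, so the central assumption is at the high end for key data. With the rarer factor and outcome, the standard error of one log-OR at n = 3,951 is about 0.17 to 0.22, so even the headline gap is about one standard error there.

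Three stronger readings are tempting, and the documents do not support them:

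- **The pair is a declared check whose disagreement will be taken as informative missingness.** Section 9.7 gives that kind of purpose only to descriptive breakdowns.
- **A planned analysis, such as aminoglycoside use and renal outcome adjusted for creatinine or age, will be spurious.** Sections 8.2 and 9.7 plan a proportion and a with-and-without tabulation, not an adjusted model.
- **Imputation must replace the complete-case rule.** Rejecting it is an openly stated choice, and under values missing completely at random it would remove no bias from the second model.

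**Conclusion.** The point holds as a defect in a contingency rule. If an adjusted model is fitted as section 9.7 describes and the covariate is a confounder, the first model can be biased even under values missing completely at random. For quantitative covariates the two models can differ with no missing data, so their difference cannot be attributed to missingness. For qualitative covariates only the 'unknown' level is at fault.

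The size is conditional on the assumptions listed in the working: with quartiles and 20% missing, about 1.20 to 1.25 against 1.00 at log-OR 0.8 and about 1.05 against 1.00 at log-OR 0.4. There is no systematic gap if the covariate is unrelated to either the factor or the outcome, so it would be wrong to infer that the two models must always disagree. The good performance of the second model assumes, as simulated, a linear effect of the covariate on the log-odds.

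The descriptive primary results, the exact intervals and the numbers 3,951 and 5,268 are untouched. The weight is modest, but the correction is simple.

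**What to change.** Amend the missing-data paragraph of section 9.7, and the SAP to match, so that for any adjusted model:

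1. the main model is the complete-case model, with a quantitative covariate kept in its quantitative form;
2. any comparison model uses the same covariate form, so that only the patient set changes;
3. 'unknown' stays as a row in descriptive breakdowns but is not used as an adjustment level.

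Multiple imputation of the covariate, in that same form, may be offered as an optional sensitivity analysis. The point does not depend on it.

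The cost is a few lines of text and no new data collection. The downside is that adjusted models lose the patients with a missing covariate, so the number excluded should be reported with each model.
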